In contrast, atypical PKAN usually becomes evident after the age of ten years and progresses more slowly. The average age at which symptoms develop is 13 years. Loss of independent ambulation often occurs 15–40 years after the initial development of symptoms. In general, atypical disease is less severe and progresses more slowly than classical PKAN. It is hypothesized that classical PKAN results from complete absence of the enzyme pantothenate kinase whereas atypical disease results from a severe deficiency; i.e., individuals retain some level of enzyme activity.

In the last decade, progress has been made in stratifying NBIA and PKAN according to gene mutations and phenotype. However, no genetic or other specific therapies are available for this condition (2, 8, 9).

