where TREAT is the indicator variable for treatment group (DFP vs. Placebo), USUBJID represents the patient ID, VISIT is the discrete variable representing the scheduled study visit after the baseline visit, DBSCHG is the discrete variable with three categories for

DBS settings change (DBS Setting Change, No DBS Setting Change, No DBS), RESMED is the binary variable for outcome impacting medication use (Yes vs. No), CHG is the change in value of efficacy outcome from baseline to the scheduled visit, BASE is the baseline value of efficacy outcome, and NDRUG is the frequency of PRN drug or rescue medication use.

PGI-I is already a measurement of change from baseline and thus will be used directly as the outcome variable and baseline BAD score will be included as the baseline value in all models.

McNemar's test will be used to compare the proportion of responders in the initial study with the proportion of responders in the extension study.

For all patients who were on DFP in both studies, the longitudinal response profile for BAD score will be explored by a MMRM model with time modelled as a continuous variable.

For this model, AR(1) (autoregressive of order 1) covariance structure will be used to model the correlation between repeated measures within the same patient and Kenward and Roger's method will be used to estimate the denominator degrees of freedom.

A sample SAS code for this MMRM model is presented in the box below:

```
proc mixed;  
  class USUBJID VISIT;  
  model BAD= TIME /solution ddfm=kr;  
  repeated VISIT/ subject=USUBJID type=ar(1);  
run;
```

where USUBJID represents the patient ID, VISIT is the discrete variable representing the scheduled study visit after the baseline visit, BAD is the value of BAD score at each time point, and TIME is the time in months at each time point corresponding to each visit.

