4.3.1 Efficacy Endpoints

All patients:

For the efficacy measures of BAD (total score and by body region) and PGI-I, the value at each of the measurement time points defined in section 4 will be determined and summarized using descriptive statistics for all patients on DFP treatment. Similar data will also be presented by the treatment group received in initial study.

A paired t-test will be used to assess the statistical significance of the changes in these efficacy outcomes from baseline to the end of study (Visit 4, month 18 or 36 as defined in section 4).

For the BAD total score and for PGI-I, the proportions of patients determined to be responders at the end of study (Visit 4) will be calculated and presented along with 95% confidence intervals.

The mean trajectory of BAD (total score and by body region) and PGI-I by time will be plotted. The longitudinal trend for BAD total score and by body region will be explored by the MMRM model with time modelled as a continuous variable as defined in section 4 for all time points where patients were on DFP.

Patients who received placebo in initial study:

For the efficacy measures of BAD (total score and by body region) and PGI-I, the value at each of the measurement time points defined in section 4 will be determined and summarized using descriptive statistics for each study period.

A paired t-test will be used to compare the change in BAD (total score and by body region) between the start and completion of the initial study to that between the start and completion of the extension study. The same test will be repeated for the PGI-I data.

The incidence of changes in DBS settings and outcome impacting medication use as well as the frequency of PRN drug or rescue medication use will be tabulated and compared between the initial study and the extension study. If statistically significant imbalances are detected, they will be adjusted accordingly for the comparison of changes in BAD and PGI-I between the initial study and the extension study by using the MMRM model as defined in section 4.

For the BAD total score and for PGI-I, McNemar's test will be used to compare the proportion of responders in the initial study with the proportion of responders in the extension study.

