Table 14.2.1.16s	Efficacy endpoints analysis for all patients on DFP: proportions of responders in BAD total score and PGI-I at the end of study (Visit 4) with imputed data – PP population
Table 14.2.1.17	Trend analysis by MMRM model on BAD total score and by body region for all patients – ITT population

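### The exploratory BAD trend model has AR(1) residuals but no patient-level intercept or slope, so its slope interval may be too narrow or too wide; SAP section 4 also names a different population from section 4.3.1 and Table 14.2.1.17

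*SAP*

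**What the plan says.** SAP section 4 gives the model as "model BAD= TIME /solution ddfm=kr", with the covariance line "repeated VISIT/ subject=USUBJID type=ar(1" (closing bracket cut from the quote). The outcome is the raw BAD score. The only fixed effects are an intercept and one common time slope. There is no RANDOM statement, baseline covariate, group term or EMPIRICAL option. The code is labelled as a sample, but the text above it also specifies AR(1) with Kenward-Roger degrees of freedom.

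Three places state the population:

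- **SAP section 4:** "For all patients who were on DFP in both studies". That is the DFP-DFP group, 44 enrolled according to SAP section 3.2.
- **SAP section 4.3.1, under the all-patients heading:** "for all time points where patients were on DFP". This brings in the 24 placebo-DFP patients.
- **Table 14.2.1.17:** "Trend analysis by MMRM model on BAD total score and by body region for all patients – ITT population". That is up to 68 enrolled, less anyone who fails the ITT definition in SAP section 3.3.

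The table shell reports a slope, its 95% CI and a p-value for the BAD total and for each body region. The protocol does not contain this model.

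**The concern.** AR(1) on visit order makes the correlation between two visits decay geometrically with the number of visits between them, and keeps the variance constant. The documents give reason to expect neither pattern. Patients are likely to differ persistently in level on a 0 to 32 scale. Protocol section 1.1.1 says that "atypical disease is less severe and progresses more slowly than classical PKAN", so progression speed should differ between patients as well.

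The two departures act in opposite directions. Without a patient intercept, AR(1) reads stable differences in level as slow drift, which inflates the slope SE. Without a patient slope, it ignores a real source of variation in the mean slope, which deflates the SE. Kenward-Roger does not correct either error, because it takes the stated covariance structure as right.

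At stake is the reliability of the interval and p-value in Table 14.2.1.17. Separately, a programmer cannot follow section 4 and section 4.3.1 at once. If that is left open, the population could be chosen after the results are known.

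**Working it through.** **Plan's own figure.** There is none to reproduce. SAP section 3.2 says that no formal sample size or power calculation was done, and no precision for the slope is stated.

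**Inputs from the documents.** 44 DFP-DFP and 24 placebo-DFP patients enrolled (SAP 3.2); analysis visits at months 6 to 36, or 6 to 18 for placebo-DFP (SAP 4); two-sided 0.05 (SAP 3.6).

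**Inputs assumed.** Between-patient SD 6 points, residual SD 1 to 2 points, slope SD 0 to 3 points/year. No dropout and no scale limits.

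**Method.**

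1. The true covariance for a patient seen at times t (years) is V = σ_b² J + σ_s² tt′ + σ_e² I, where J is the all-ones matrix.
2. The AR(1) matrix S that the SAP model converges to minimises log|S| + tr(S⁻¹V).
3. With X = [1, t] and A = n X′S⁻¹X, the model-based variance of the slope is the time element of A⁻¹.
4. The true variance is the same element of A⁻¹BA⁻¹, with B = n X′S⁻¹VS⁻¹X.
5. With r = model SE / true SE, the actual error rate of a nominal 5% test is 2Φ(−1.96 r).

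**Worked case.** For slope SD 3 and residual SD 1, the model SE is 0.245 and the true SE 0.458 points/year. So r = 0.245/0.458 ≈ 0.535, and the error rate is 2Φ(−1.049) ≈ 29%.

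**Results for 44 patients, months 0 to 36, between-patient SD 6** (r, then actual error rate):

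| Slope SD (points/year) | Residual SD 1 | Residual SD 1.5 | Residual SD 2 |
|---|---|---|---|
| 0 | 2.37, about 0% | 2.29, about 0% | 2.19, about 0% |
| 1 | 1.07, 3.6% | 1.36, 0.8% | 1.53, 0.3% |
| 1.5 | 0.80, 11.5% | 1.04, 4.2% | 1.21, 1.7% |
| 2 | 0.67, 19.2% | 0.85, 9.6% | 1.01, 4.9% |
| 3 | 0.54, 29.4% | 0.65, 20.1% | 0.77, 13.3% |

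**Sensitivity.** Widening the grid to between-patient SD 4 to 8 and residual SD 1 to 3 gives r from 0.53 to 2.40. With post-baseline visits only, r runs from 0.58 to 2.20. With all 68 patients it runs from 0.55 to 2.18.

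**Simulation check** (2000 trials per setting, REML AR(1) fit, t interval with 150 df standing in for Kenward-Roger). For 44 patients, coverage was 100% at slope SD 0 / residual SD 1.5, 96.1% at 1.5/1.5, 81.4% at 2/1 and 70.5% at 3/1.

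**Control.** When the data truly followed AR(1), with correlation 0.8 or 0.95, the same fit covered 95.4% and 95.9% (1000 trials each). The error therefore comes from the covariance structure.

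**With a random intercept and slope** (400 trials per setting, t with 43 df). At slope SD / residual SD of 0/1.5, 1/1.5, 2/1 and 3/1, coverage was 95.0%, 94.0%, 94.8% and 94.3% for 44 patients, and 96.0%, 95.8%, 95.8% and 96.5% for 68. As a check on the SE, for balanced data it should be about √[(σ_s² + σ_e²/Σ(t−t̄)²)/n], with Σ(t−t̄)² = 7 for visits at 0, 0.5, …, 3 years. At 2/1 this is √[(4 + 1/7)/44] = 0.307, against a simulated mean of 0.306.

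**Population.** This part needs no assumption: 44 enrolled under section 4, and 44 + 24 = 68 under section 4.3.1 and the table. If all 68 enter, months 24 to 36 come only from DFP-DFP patients, and the model has no group term.

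**The case against.** **The analysis is exploratory.** This stands. Sections 4 and 4.3.1 both say the trend will be explored, and no slope is among the listed endpoints. The BAD endpoint is change from baseline to Visit 4, tested by paired t-test, and the primary objective is safety. A reader might infer that this slope is the SAP's summary of long-term dystonia progression. The documents do not support that.

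**The size is driven by assumptions.** This largely stands. Protocol section 1.1.1 also calls most cases classical and fairly homogeneous in phenotype, although phenotype is not slope. If a 50/50 mix of two forms were the only source of slope variation, slope SD 3 would need a gap of 2 × 3 = 6 points/year, or 18 points over 36 months on a 0 to 32 scale. With an assumed baseline mean of 16, mean slope 1/year, between-patient SD 6 and residual SD 1, month-36 scores have mean 19 and SD √(36 + 81 + 1) ≈ 10.9, so about 16% fall outside the scale. The extreme corner is therefore strained. Slope SD 2 with residual SD 1 remains possible, and there the error rate is about 19%.

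**When slopes vary little, the error is only conservative.** In the table, r is 1.07 or more whenever slope SD is 1 or less. The intervals are then too wide, which costs precision and does not create false positives.

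**Heterogeneity is shown elsewhere.** The SAP plans subgroups by age at onset and disease duration, and per-patient BAD plots. These display the variation but do not correct the slope SE.

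**The population conflict is one stray sentence.** This is mostly right. A reader might infer that two different slopes could be reported under one heading. Only one trend table is planned, however, and it agrees with section 4.3.1. The section 4 sentence is the one out of line.

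**Conclusion.** The point holds as a low-priority correction. As specified, the interval and p-value for the BAD slope rest on a covariance structure that leaves out two features the documents give reason to expect, and they may be wrong in either direction. Under the assumed values the model SE is about 0.54 to 2.4 times the true SE, and the nominal 5% test has an actual rate of about 0% to 29%.

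A reader might go further and say that the interval does not have its stated coverage. The documents give no variance components, several plausible settings are close to nominal (r of 1.01 to 1.07), and AR(1) would be adequate if it were true. So neither the direction nor the size of the error in this trial can be determined.

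The population conflict rests on the text alone. The figures 44 and 68 are enrolled counts, so the ITT numbers actually fitted may be smaller. The listed BAD endpoint tests are unaffected.

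**What to change.** 1. **Covariance.** Replace the AR(1) REPEATED statement with `random intercept TIME / subject=USUBJID type=un;`. If this does not converge for a single-region score, use EMPIRICAL standard errors and name a degrees-of-freedom method other than `ddfm=kr`, which is a model-based correction.
2. **Population.** Change the section 4 sentence to match section 4.3.1 and Table 14.2.1.17: all on-deferiprone time points of ITT patients.
3. **Baseline.** State whether the baseline score is an outcome record in this model. Section 4 defines VISIT as post-baseline while using the raw score, so this is unclear.
4. **Late visits.** Because months 24 to 36 come only from DFP-DFP patients, include a term for initial treatment group, or also report the DFP-DFP slope separately.

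The cost is a small code change and a few sentences, plus one extra slope if it is reported separately. No new data are needed. The downside is possible non-convergence for single-region scores, which the fallback in step 1 covers.

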4.1 Patient Dispositions and Drug Exposure

Patient disposition, based on the ITT population, will be summarized and presented, including the number and percentages of patients who were enrolled, completed the study, and withdrew (including reasons for withdrawals).

For each patient, the compliance on the study drug will be computed from the study drug dispensing and accountability eCRFs obtained at each visit. The extent of exposure to the study medication taken during the study and the compliance will be summarized with descriptive statistics.

The number of enrolled patients for each study site will be presented and the number of subjects included in each population will be tabulated.

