9 STATISTICAL ANALYSIS

9.1 Endpoints

9.1.1 Primary Endpoints

- Adverse events (AEs): Frequency, severity, time to onset, duration, and relatedness to study product

- Serious adverse events (SAEs): Frequency, severity, time to onset, duration, and relatedness to study product
- Number of discontinuations due to AEs
- Hematology assessments
- Blood chemistry assessments
- ECG assessments

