9.4.1 Planned Analyses

9.4.1.1 Patient Disposition and Drug Exposure

Patient disposition will be summarized and presented, including the number and percentages of patients who were enrolled, completed the study, and withdrew (including reasons for withdrawals).

For each patient, the number of doses taken will be computed from the study drug dispensing and accountability eCRFs obtained at each visit. The extent of exposure to the study medication as well as the number of doses taken during the study will be summarized with descriptive statistics.

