3.3 Analysis Populations

The following study populations will be used for analysis: Safety, Intent-to-Treat (ITT), and Per-Protocol (PP). The safety population will be used for the analysis of safety endpoints. The ITT population will represent the primary analysis population for the evaluation of efficacy endpoints, and the PP population will be the secondary efficacy analysis population.

Safety Population

The Safety population will include all patients who took at least one dose of study drug in the extension study.

ITT Population

The ITT population will include all enrolled patients who received at least one dose of study drug and have a baseline and at least one post-baseline efficacy assessment in the extension study.

PP Population

The PP population will include all enrolled patients who complete the extension study and have an efficacy assessment at the end of the study, have no major protocol violations, and have no change in DBS and baclofen pump settings or medications that could have an impact on dystonia. Prior to database lock, protocol deviations and medications that could have an impact on dystonia will be reviewed for their seriousness, and patients with major deviations will be excluded from the PP population.

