14.1 Disposition, Demographics and Baseline Data

Table 14.1.1	Number of patients in different populations
Table 14.1.2	Subject disposition – ITT population
Table 14.1.3	Subject exposure to study medication – ITT population
Table 14.1.4	Number of patients enrolled by study site – ITT population
Table 14.1.5	Summary of the reasons for not completing the study – ITT population
Table 14.1.6	Summary of demographics data at baseline of initial study – ITT population
Table 14.1.6a	Summary of demographics data at baseline of initial study – PP population
Table 14.1.7	Summary of baseline characteristics at the initial study – ITT population
Table 14.1.7a	Summary of baseline characteristics at the initial study – PP population

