Completed	xx	xx	xx
Withdrawn	xx	xx	xx

Table 14.1.3 Subject exposure to study medication – ITT population

	Group		
	Placebo-DFP (N=xx)	DFP-DFP (N=xx)	Overall (N=xx)
Subjects Exposed	xx	xx	xx
Total Exposure (person-years)	xxx.x	xxx.x	xxx.x
Length of Exposure (years)			
Mean (SD)	xx.xx (xx.x)	xx.xx (xx.x)	xx.xx (xx.x)
Median	xx.x	xx.x	xx.x
(Min, Max)	(xx.x, xx.x)	(xx.x, xx.x)	(xx.x, xx.x)
Duration of Exposure [n(%)]			
>= 1 month	xx (xx)	xx (xx)	xx (xx)
>= 6 months	xx (xx)	xx (xx)	xx (xx)
Repeat for 9, 12, 15, 18 months

Table 14.1.4 Number of patients enrolled by study site – ITT population

Country	Site	Group		
		Placebo-DFP	DFP-DFP	Overall
xxx	000x	xx	xx	xx
...	...	xx	xx	xx
Total	x	xx	xx	xx

Table 14.1.5 Summary of the reasons for not completing the study – ITT population

		Group		
		Placebo-DFP (N=xx)	DFP-DFP (N=xx)	Overall (N=xx)
Reason	Detail	n (%)	n (%)	n (%)
Adverse event	Ccccc	xx (xx)	xx (xx)	xx (xx)
	Ccccc	xx (xx)	xx (xx)	xx (xx)
Voluntary withdrawal	Ccccc	xx (xx)	xx (xx)	xx (xx)
	Ccccc	xx (xx)	xx (xx)	xx (xx)
Lost to follow up	Ccccc	xx (xx)	xx (xx)	xx (xx)
	Ccccc	xx (xx)	xx (xx)	xx (xx)
Investigator decision	Ccccc	xx (xx)	xx (xx)	xx (xx)
	Ccccc	xx (xx)	xx (xx)	xx (xx)
Protocol violation	Ccccc	xx (xx)	xx (xx)	xx (xx)
	Ccccc	xx (xx)	xx (xx)	xx (xx)
Worsening of the disease/ Lack of efficacy	Ccccc	xx (xx)	xx (xx)	xx (xx)
	Ccccc	xx (xx)	xx (xx)	xx (xx)
Other	Ccccc	xx (xx)	xx (xx)	xx (xx)
	Ccccc	xx (xx)	xx (xx)	xx (xx)
Total		xx (xx)	xx (xx)	xx (xx)

Demographics and baseline characteristics tables

Table 14.1.6 Summary of demographics data at baseline of initial study – ITT population

	Group			
	Placebo-DFP (N=xx)	DFP-DFP (N=xx)	Overall (N=xx)	DFP vs Placebo p -value [§]
Age (years) (Mean ± SD) (Minimum, Median, Maximum)	xx.x ± xx.x (xx.x, xx.x, xx.x)	xx.x ± xx.x (xx.x, xx.x, xx.x)	xx.x ± xx.x (xx.x, xx.x, xx.x)	0.xxxx
Sex: n (%) Female Male	xx (xx) xx (xx)	xx (xx) xx (xx)	xx (xx) xx (xx)	0.xxxx
Racial Origin: n (%) White Black Asian Native American Native Hawaiian or Other Pacific Islander Multi-Racial	xx (xx) xx (xx) xx (xx) xx (xx) xx (xx) xx (xx)	xx (xx) xx (xx) xx (xx) xx (xx) xx (xx) xx (xx)	xx (xx) xx (xx) xx (xx) xx (xx) xx (xx) xx (xx)	0.xxxx
Ethnic Origin: n (%) Hispanic/Latino Other	xx (xx) xx (xx)	xx (xx) xx (xx)	xx (xx) xx (xx)	0.xxxx

§ T-test for means and Fisher's exact test for percentages

Similar Table 14.1.6a will be based on PP population

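### Disposition, exposure, site and withdrawal-reason tables use an ITT set that can leave out dosed early leavers, so they may disagree with the Safety-set tables

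*SAP*

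**What the plan says.** SAP 4.1 opens with "Patient disposition, based on the ITT population, will be summarized and presented", and that summary includes the reasons for withdrawal. SAP section 5 labels Tables 14.1.2 to 14.1.5 in the same way, for example "Subject exposure to study medication – ITT population" (Table 14.1.3) and "Summary of the reasons for not completing the study – ITT population" (Table 14.1.5).

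Under SAP 3.3, ITT patients must be enrolled, have taken at least one dose, and "have a baseline and at least one post-baseline efficacy assessment in the extension study". The Safety set is wider: "The Safety population will include all patients who took at least one dose of study drug in the extension study".

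Protocol 9.4.1.1 asks for "the number and percentages of patients who were enrolled, completed the study, and withdrew (including reasons for withdrawals") and names no analysis set. Protocol 9.1.1 lists "Number of discontinuations due to AEs" among the primary endpoints. SAP 4.4 puts every safety endpoint on the Safety set, and the shell of Table 14.3.1.1 has rows for patients withdrawn and for withdrawals due to AE. SAP 4.4.1 also promises a frequency table of the AEs that led to withdrawal, a listing and narratives.

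**The concern.** A disposition table should account for everyone who entered. Here a patient can be removed from the withdrawal tables as a consequence of withdrawing early. On a set that already requires enrolment and a dose, the Enrolled and Exposed rows of Table 14.1.2 both equal the ITT count and tell the reader nothing. If anyone fails the ITT condition, the Enrolled row will contradict the 68 enrolled in SAP 3.2, and Table 14.1.4 has the same fault.

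The study's primary objective is long-term safety and tolerability, so these tables support the main message. Three things are at stake:

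- **Reasons for withdrawal.** None of the listed Tables 14.3.1.1 to 14.3.1.8 is the promised summary of AEs leading to withdrawal. Table 14.1.5, with its adverse-event detail rows, is the only numbered summary table that shows them, and it is on ITT.
- **The split by prior treatment.** Table 14.3.1.1 has a single deferiprone column. Only the ITT tables separate switchers from continuers.
- **Exposure.** Table 14.1.3 gives person-years on ITT, while the AE rates per 100 patient-years use Safety-set exposure.

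**Working it through.** The plan has no figure to reproduce on this point; SAP 3.2 says that no sample size was calculated. The enrolment split agrees with the total: 44 + 24 = 68.

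**When can a patient first meet the ITT condition?** Protocol Table 5.1 schedules BAD at Visit 1, Weeks 26, 52 and 78, and early termination. PGI-I has the same schedule without Visit 1. The protocol synopsis assigns the Visit 1 PGI-I to the initial study only.

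- *Switchers (24).* Visit 1 is their baseline (SAP section 4). Their first post-baseline assessment is at Week 26 or at early termination.
- *Continuers (44).* Their baseline lies in the initial study, and Protocol 7.1.1 counts the Visit 1 BAD among the extension's assessments. Read literally, they meet the condition at Week 0. If Visit 1 is not meant to count, they are in the same position as switchers. The SAP does not say which applies.

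**Is an early-termination assessment certain?** No. Protocol 4.5 says that withdrawn patients should return for that visit, and Protocol 7.2.2 says that end-of-study procedures are to be done there. This is an expectation, and it cannot cover a patient who dies or does not return.

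**Direction.** Let W be all withdrawals and k those left out, assuming that all 68 were dosed and nobody else fails the ITT condition. The withdrawal share moves from W/68 to (W − k)/(68 − k), which is never larger. The completion share moves from (68 − W)/68 to (68 − W)/(68 − k), which is never smaller.

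**Size per omitted patient.** 1/68 = 1.5% of all patients; 1/24 = 4.2% of switchers.

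**Illustration for the AE rows of Table 14.1.5.** D is the number of AE withdrawals and k the number of those left out. Both are assumptions.

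| k | All patients, D = 4 (Safety set 4/68 = 5.9%) | Switchers, D = 3 (Safety set 3/24 = 12.5%) |
|---|---|---|
| 0 | 4/68 = 5.9% | 3/24 = 12.5% |
| 1 | 3/67 = 4.5% | 2/23 = 8.7% |
| 2 | 2/66 = 3.0% | 1/22 = 4.5% |
| 3 | 1/65 = 1.5% | 0/21 = 0% |

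If the omitted patient left for another reason, the AE count stays the same and its percentage rises slightly: 4/67 = 6.0% against 4/68 = 5.9%. The one-way direction therefore holds for withdrawals overall, and for the AE rows when the omitted patients left because of AEs.

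**Is an early toxicity withdrawal plausible?** Protocol 1.3 gives agranulocytosis in about 1.7% of patients in pooled trials and describes the safety profile as characterised in systemic iron overload. Protocol 4.5 makes agranulocytosis a mandatory withdrawal. Applied to the 24 switchers, 24 × 0.017 = 0.41 cases are expected, and the chance of at least one is 1 − 0.983^24 = 33.7%. This is the chance of such a withdrawal. It does not give the chance that the patient also lacks an efficacy assessment.

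**Person-years.** A switcher who leaves before Week 26 contributes less than 26/52 = 0.5 year. Three such patients would take less than 1.5 person-years from a planned 24 × 1.5 = 36, or less than 4.2%.

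**Exposure bands.** The Table 14.1.3 shell says "Repeat for 9, 12, 15, 18 months" and goes no further. SAP 3.5 starts all duration calculations for continuers at their first dose in the initial study. On that clock they have about 18 months behind them at entry, so every band would read close to 100% for 44 of 68 patients. SAP 4.1, however, speaks of exposure during the study, which could mean the extension alone.

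**The case against.** A reader might infer that patients who stop for toxicity vanish from the primary endpoint. The documents do not support that. Discontinuation due to AEs is a safety endpoint on the Safety set, Table 14.3.1.1 counts it, and SAP 4.4.1 adds a frequency table, a listing and narratives.

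A reader might also infer that the gravest events are the likeliest to be lost, because Protocol 7.2.1.8 mentions an early termination visit under moderate neutropenia but not under agranulocytosis. That is a selective reading. Protocol 4.5 and 7.2.2 cover every withdrawal, and the visit includes BAD and PGI-I. Hospitalisation alone neither withdraws a patient nor rules out a later assessment.

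Other points against the concern are fair. Table 14.1.1 prints ITT and Safety counts by prior treatment, and listings of disposition and of assignment to analysis sets are planned, so a gap would be visible. SAP section 5 allows tables to be added, so the missing table of AEs leading to withdrawal is a gap in the list and not a withdrawn commitment. No document says how many patients would be affected.

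These points limit the harm but do not remove the fault. Table 14.1.1 shows that someone is missing but not why that patient left. A listing does not replace a disposition summary with the right denominator. The doubt over Visit 1 for continuers, if settled in favour of counting it, would concentrate any omission among the 24 patients new to deferiprone.

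**Conclusion.** The point holds as a correction to the population of four supporting tables. Following SAP 4.1 as written can omit dosed early leavers from disposition, exposure, site and withdrawal reasons, a restriction that Protocol 9.4.1.1 does not make. Each omitted patient is 1.5% of all patients or 4.2% of switchers, and the effect is to understate withdrawal and overstate completion. The number is unknown; if it is zero, the two sets agree.

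The size rests on all 68 patients having been dosed and on early leavers being the only ones to fail the ITT condition. For continuers it also rests on the Visit 1 BAD not counting as post-baseline. The primary count in Table 14.3.1.1 stands either way, so the main safety result does not depend on this change. The exposure-band point is conditional on Table 14.1.3 using the first-deferiprone-dose clock.

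**What to change.** - In SAP 4.1, replace the ITT basis: disposition and enrolment by site on all enrolled patients; exposure and reasons for not completing on the Safety set (or all enrolled). Retitle Tables 14.1.2 to 14.1.5 to match.
- Require the AE rows of Table 14.1.5 to reconcile with the row for withdrawals due to AE in Table 14.3.1.1, and the person-years of Table 14.1.3 with the exposure in the AE table headers.
- Give a table number to the Safety-set frequency table of AEs leading to withdrawal that SAP 4.4.1 promises.
- State in SAP 3.3 whether the Visit 1 BAD satisfies the ITT condition for continuers.
- State which exposure clock Table 14.1.3 uses. If it runs from the first deferiprone dose, extend the bands to 24, 30 and 36 months.

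The cost is SAP wording, table titles and one additional numbered table, with no new data. The one downside is that the reported completion rate may look slightly less favourable.
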